Insertion of mesh or other prosthesis for repair of pelvic floor defect 57267

General Prolapse Repair codes:

Repair of cystocele and rectocele, no graft 70.50 Repair of cystocele, no graft 70.51 Repair of rectocele, no graft 70.52 Other operations on cul-de-sac (repair of vaginal enterocele), no graft 70.92 Vaginal construction, no graft 70.61 Vaginal reconstruction, no graft 70.62 Vaginal suspension and fixation, no graft 70.77 Colpocleisis 70.80 Other uterine suspension 69.22 Vaginal repair of chronic inversion of uterus 69.23 Other repair of uterus and supporting structures 69.29 Other operation on supporting structure of the uterus 69.98 Obliteration of vaginal vault and total excision of vagina 70.4

General Prolapse CPT-4 Codes:

Rectocele repair 45560 Anterior colporrhaphy, repair of cystocele 57240 Posterior colporrhaphy, repair of rectocele 57250 Combined anteroposterior colporrhaphy with enterocele repair 57265 Combined anteroposterior colporrhaphy 57260 Synthetic Mid-Urethral Slings for Stress Urinary Incontinence in Women Protocol 1 Enterocele Repair—vaginal approach 57268 Enterocele Repair — abdominal approach 57270 Colpocleisis 57120 Colpopexy, vaginal, extraperitoneal approach 57282 Colpopexy, vaginal, intraperitoneal approach 57283 Insertion of mesh; vaginal approach 57267 Pereyra procedure, including anterior colporrhaphy 57289 Removal or revision of sling for SUI 57287 Revision (including removal) of prosthetic vaginal graft; vaginal approach 57295 Sling operation for SUI 57288 Uterine suspension 58400 Uterine suspension 58410 Vaginal hysterectomy, with repair of enterocele 58270 Vaginal hysterectomy, with colpourethrocystopexy, complicated 58293 Vaginal hysterectomy with repair of enterocele, complicated 58294

Sling Codes:

Retropubic Urethral Suspension 59.4, 59.71, 59.79 *Must be used concurrently with other prolapse repair codes.

International Classification of Diseases (ICD)-9/10 Diagnosis and Procedure Codes ⁵⁶

Diagnoses

Urinary incontinence	625.6/N39.3 Stress urinary incontinence, female
	599.82/N36.42 Intrinsic sphincter deficiency
	788.30/R32 Urinary incontinence, unspecified
	788.31/N39.41 Urge incontinence
	788.32/N39.3 Stress urinary incontinence, male
	788.33/N39.46Mixed incontinence (male) (female)
	788.34/N39.42 Incontinence without sensory awareness
	788.35/N39.43Post-void dribbling
	788.36/N39.44 Nocturnal enuresis
	788.37/N39.45 Continuous leakage
	788.38/N39.490 Overflow incontinence
	788.39/N39.4 Other urinary incontinence
Prolapse	618.01/N81.11 Cystocele, midline
	618.02/N81.12 Cystocele, lateral
	618.03/N81.0 Urethrocele
	618.81/N81.82 Incompetence or weakening of pubocervical fascia
	618.1 Uterine prolapse without mention of vaginal wall prolapse
	618.2/N81.2 Uterovaginal prolapse, incomplete
	618.3/N81.3 Uterovaginal prolapse, complete
	618.4/N81.4 Uterovaginal prolapse, unspecified
	618.5/N99.3 Prolapse of vaginal vault after hysterectomy
	618.6/N81.5 Vaginal enterocele, congenital or acquired
	618.94/N81.85 Cervical stump prolapse
	618.04/N81.6 Rectocele
	618.05/N81.81 Perineocele
	618.82/N81.83 Incompetence or weakening of rectovaginal fascia
	618.00/N81.4Unspecified prolapse of vaginal walls
	618.09/N81.89 Other prolapse of the vaginal walls without mention of utering
	prolapse

	618.7/N88.1 Old laceration of muscles of pelvic floor
	618.83/N81.84 Pelvic muscle wasting
	618.89/N81.89 Other specified genital prolapse
	618.9/N81.9 Unspecified genital prolapse
Surgical Complications	629.31/T83.711 Erosion of implanted vaginal mesh
	629.32/T83.721 Exposure of implanted vaginal mesh
	996.76/T83.9 Complication of genitourinary device, implant or graft
	V58.2 Blood transfusion
	998.5 Postoperative infection
	778.2/R33.9 Urinary retention

Procedures

SUI Procedures – Sling	59.4/ OTSC4ZZ Suprapubic sling operation 59.79/ OTQD3ZZ Pubovaginal sling; Anterior urethropexy; Repair of stress incontinence NOS
SUI Procedures - Burch	59.5/ 0TSD4ZZ, 0TSD0ZZ Retropubic urethral suspension (Burch)
SUI Procedures - Other	59.6/ OTSC4ZZ, OTSCOZZ Paraurethral suspension
Soff foreduces of the	59.71/ OTUCOKZ Levator muscle operation for urethrovesical suspension
	59.72/ 3E0K4GC Injection of implant into urethra and/or bladder neck
Anterior Repair	70.51/ 0JQC0ZZ, 0JQC3ZZ Repair of cystocele
	70.54/ 0JUC07Z, 0JUC0JZ, 0JUC0KZ, 0JUC37Z, 0JUC3JZ, 0JUC3KZ Repair of
	cystocele with graft or prosthesis
Posterior Repair	70.52/ 0JQC0ZZ, 0JQC3ZZ Repair of rectocele

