Next, if the characterization of the data is sufficient for the task, we will pursue a Cox proportional hazards model analysis, with each of the outcomes assessed from the time of the surgery as a time-to-event. We will censor the time-to-event analysis with death or loss to follow-up, defined as a time period >2 years from last applicable encounter of primary care, Obstetrics & Gynecology, or Urology. The models will first be developed at each institutional separately using LASSO Cox to predict time to event for each of the outcomes of interest. We will use the variables retained in any of the individual site models, and develop a Cox model using the method described by Lu and colleagues (WebDISCO) that uses a distributed analysis approach to obtain an exact model solution without sharing case level data (only intermediate and aggregate model coefficients and matrices)¹. This method is being used to protect patient data by processing it at the local institutions and only sharing intermediate modeling statistics (aggregates) between sites.

Because bootstrapping combined with the distributed analysis method would be computationally intensive, we will utilize 10-fold cross validation across all sites for internal validation of the risk model. We assessed overall discrimination using Harrell's concordance statistic (C-statistic). To provide calibration assessments, we will also evaluate the model at fixed time points of 1 year and 2 year for each outcome using the AUC and the Estimated Calibration Index (ECI). The ECI looks at the squared difference between the predicted probability and an estimated observed probability, ranging between 0 and 100, with 0 meaning perfect calibration. Additionally, we will graphically analyze calibration by investigating the smoothed observed-to-predicted probability plot.

Target Population:All women aged 18 or greater undergoing transvaginal surgery for stress
urinary incontinence with or without mid-urethral mesh sling implantation
are eligible for inclusion in the EHR data. Determination of the appropriate
mesh exposure during surgery will be determined through administrative
CPT procedure codes, as defined in the appendix. No exclusions will be
applied based on race or ethnicity. As a separate sensitivity analysis to
reduce potential lack of outcome ascertainment, we will exclude all
patients that do not also have continuity of care within the data site,

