5. TARGET POPULATION

Inclusion criteria:

- All women aged 18 or greater undergoing transvaginal surgery for stress urinary incontinence (index surgery) with or without mesh implantation
- EHR-Based study date range 2010-2019
- Inpatient or outpatient visit

Exclusion criteria:

- No primary care, ob/gyn, or urology visits in the year prior to the surgery
- Prior pelvic organ prolapse surgery
- Prior stress urinary incontinence surgery
- Prior surgery diagnosis of a urethral diverticulum ICD-9-CM code 619.0 or any urinary-genital tract fistula (codes 599.1 and 599.2) in the 90 days prior to the index surgery.

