8.1 DATA COLLECTION AND MANAGEMENT

As shown in Figure 1, we will access the data in each institution through the PCORNet or OMOP common data models, which are a normalized sub-set of EHR data that allows standardization of data representation and analytic processes. All sites but Lahey have PCORNet instituted through participation in PCORNet, and Lahey has OMOP. There is a publicly available transform from OMOP to PCORNet that will be utilized to harmonize Lahey to PCORNet. The data available across all sites is limited to patient demographics, inpatient and outpatient administrative condition and procedure codes (ICD-9/10, ICD-9/10 Procedure, CPT, HCPCS, SNOMED-CT), medication orders and/or fills/administrations, laboratory test results, vital signs, and date of death. We prefer prescribing if both are available. The PCORNet common data models in each site except Lahey have undergone extensive data quality assessment through data characterization queries where gaps and systematic miscoding have been reported and addressed over the course of the PCORNet CDRN network lifespan.

[figure not shown]

Figure 1: Summary of data collection and data flow process at each site for the variable transformation and distributed regression portions of the project.

Each of the participating sites will supplement their existing CDM-based structured data with free text peri-operative documents for those patient cases that has mesh implantation for stress urinary incontinence, as defined and identified elsewhere. As procedural codes are date specific, all documents +/- 2 days of the administrative code date will be extracted. Notes will then be further filtered to include only 2 notes for each surgical case, the pre-operative planning note (Surgeon, Anesthesia, or Nursing) and the operative note. Sample size estimates are based on a number of referent publications.^{50,51} Each site will randomize their patient population and initially select 600 patient documents among 300 patients (2 documents per patient, the primary operative note and a random note from the other notes included) for each surgery. Each site will determine what the surgical approach is at the document level (document assignment) and patient level (merging the 2 document assignments). Vanderbilt will annotate an additional 100 patients to serve as the primary training data set (100 training, 100 internal validation).

Version 2.0 [15 July 2020]

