13. APPENDICES

Synthetic Mid-Urethral Slings for Stress Urinary Incontinence in Women Appendix: Data Collection

Category	Name	Definition, structured?	CDM?	Notes
Covariate	Age @ Procedure	Age as difference between date of surgery and date of birth	Yes- derived to remove PHI	
Outcome	Date of Death	The date on which the patient died.	Yes	Capture as date/time Lahey Comments: Captured only within institution, working on linkage to the SSI Death Index, otherwise would need chart review. Death status is more easily ascertained but not the death of death.
Inc/Excl Criteria	Surgery Indication (POP vs SUI)	Structured Codes Include Sling CPT: 57288 Include Lap sling CPT: 51992	Yes	CPT: 57288 includes retropubic midurethral slings, transobturator slings, and minislings,

Protocol 1				[15 July 2020]
				single-incision sling, adjustable sling CPT: 51992 includes laparoscopy approach.
Exposure	Mesh Implantation	Yes/No	Yes	Key Exposure
Covariate	Gender	Gender	Yes	
Covariate	Race	White, Black or African American, American Indian or Alaska Native, Asian, Native Hawaiian or Other Pacific Islander	Yes	
Covariate	Ethnicity	Hispanic or Non-Hispanic	Yes	
Covariate	Women's Health History: pregnancies, vaginal deliveries, and menopausal status ⁵²	Look for Gravida/Parity in problem list: ex: G3P3? Possible administrative codes: Grand multipara status only (not pregnant) ICD9/10- V61.5/Z64.1 Grand multiparity SNOMED- 364325004/452221000000100/ 440681000000102 # Parity LOINC- 11977-6 Unspecified menopausal and post-menopausal disorder ICD 9/10 627.9/N95.9 Premature menopause ICD9/10 256.31/E28.31 Post-menopausal bleeding ICD 9/10 627.1/N95.0	Partial, Admin Codes	May miss portion of data if admin codes only

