		 Mesh exposure and erosion (ICD9/10 629.31, 629.32/T83.711, T83.721) Urinary Retention (CPT Code 53500, ICD 9/10 788.20, 788.21/R33.0, R33.8-R33.9) Urgency of urination (ICD9/10 788.63/R39.15) Urge incontinence (ICD9/10 788.31/N39.41) Bowel injury (ICD9/10 569.83/S36) Bladder/urethral injury (ICD9/10 596.6,867.0/S37) Infection (ICD9/10 686.9,998.5,999.3,998.51,998.59/T81) Retropubic hematoma (ICD 9/10 568.81,,568.81,459.0/K66.1) Retopubic hematoma (ICD 9/10 568.81,,568.81,459.0/K66.1) Retopubic hematoma (ICD 9/10 568.81,568.81,459.0/K66.1) Bulking Injection CPT 51715, ICD 9/10 59.72/ PCS 3E0K3GC Laparoscopic Retropubic Urethropexy CPT 51990, 51992, 51999 Abdominal Retropubic Urethropexy CPT 51840,51841 Needle Bladder Neck Suspension CPT 51845 Kelly plication CPT 57220 Cystourethroplasty CPT 51800 Subtypes: Stress incontinence, female/mixed incontinence (ICD9/10 625.6,788.33/N39.46) Stress incontinence (female) (male)(ICD10 CM N39.3) 		
Outcome	Mesh Removal	 General, CPT 57287-Removal or revision of sling for stress incontinence (fascia or synthetic) ***some erosions managed surgically may have been coded by a different CPT (i.e. 57295 revise vaginal graft via vaginal approach) and not CPT 57287, which indicates a sling revision/removal. 	Yes	Possible Options: (a surgery for any kind of mid-urethral sling, urethral bulking agent, black neck pubovaginal sling (autologous or allograft), or revision for mesh exposure). Represented as a Date, allows time-to-event analysis.
Outcome	Post-Procedural Pain	?, mix of vital sign (pain score >3 of 10 on vital sign data) and likely free text. Also, diagnosis codes related to abd/pelvic pain (if prior pain free).	Some portion	Would have to exclude prior chronic pain or detect specific mention of new pain (free text). Could analyze group with no pre-surgical pain,

Protocol 1				[15 July 2020]
				otherwise probably beyond scope. Date/Time of first post- op occurrence.

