		N39.498 Other specified urinary incontinence		
		Prolapse		
		ICD 9:		
		618.01 Cystocele, midline		
		618.02 Cystocele, lateral		
		618.03 Urethrocele		
		618.81 Incompetence or weakening of		
		pubocervical fascia		
		618.1 Uterine prolapse without mention of		
		vaginal wall prolapse		
		618.2 Uterovaginal prolapse, incomplete		
		618.3 Uterovaginal prolapse, complete		
		618.4 Uterovaginal prolapse, unspecified		
		618.5 Prolapse of vaginal vault after		
		hysterectomy		
		618.6 Vaginal enterocele, congenital or acquired		
		618.84 Cervical stump prolapse		
		618.04 Rectocele		
		618.05 Perineocele		
		618.82 Incompetence or weakening of		
		rectovaginal fascia		
		618.00 Unspecified prolapse of vaginal walls		
		618.09 Other prolapse of the vaginal walls		
		without mention of uterine prolapse		
		618.7 Old laceration of muscles of pelvic floor		
		618.83 Pelvic muscle wasting		
		618.89 Other specified genital prolapse		
		618.9 Unspecified genital prolapse		
		ICD-10 CM :		
		N81.0 Urethrocele		
		N81.10 Cystocele, unspecified		
		N81.11 Cystocele, midline		
		N81.12 Cystocele, lateral		
		N81.2 Incomplete uterovaginal prolapse		
		N81.3 Complete uterovaginal prolapse		
		N81.4 Uterovaginal prolapse, unspecified		
		N81.5 Vaginal enterocele		
		N81.5 Vaginal enterocele		
		N81.89 Other female genital prolapse		
		N99.3 Prolapse of vaginal vault after		
	1	1953.5 I TOTAPSE OF VAGITAL VAULT ALLEL	1	1
		hysterectomy		
		hysterectomy		
Exposure	SUI with Mesh	Admin Codes CPT 57288	Yes	Capture as date/time

Version 2.0 [15 July 2020]

Protocol 1				[15 July 2020]
Exposure	SUI without Mesh	Admin Codes	Yes	Capture as date/time
	IVIES11	CPT/ICD-9-CM/ICD-10-PCS 51715/ 59.72/3E0K3GC, 3E0K4GC Injection of implant into the urethra and/or bladder neck (collagen implant)		
		CPT/ICD-9-CM/ICD-10-PCS 51990, 51992/59.5/OTSD0ZZ, OTSD4ZZ Laparoscopic urethral suspension, laproscopic sling procedure		
		CPT/ ICD-9-CM/ICD-10-PCS 51841, 51840/ 59.5/0TSD0ZZ, 0TSD4ZZ Anterior vesicourethropexy, or urethropexy (eg, Marshall- Marchetti-Krantz, Burch)		
		CPT/ICD-9-CM/ICD-10-PCS 51845/59.5/0TSD0ZZ, 0TSD4ZZ Abdominovaginal vesical neck suspension		
		CPT /ICD-9-CM/ICD-10-PCS 57220/ 59.3/0TSC0ZZ, 0TSC4ZZ Kelly plication of urethrovesical		

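### CPT 51992 slings are classed as non-mesh whatever they are made of, and the planned operative-note extraction would not correct this

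*Protocol*

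**What the plan says.** The Synopsis (Target Population) makes the appendix code lists operative: "mesh exposure during surgery will be determined through administrative" CPT codes, as the appendix defines them.

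In the Data Collection table of Section 13, CPT 51992 appears in three rows:

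- **Inc/Excl Criteria, Surgery Indication:** "Include Lap sling CPT: 51992", beside 57288, with the note "CPT: 51992 includes laparoscopy approach".
- **Exposure, SUI without Mesh:** "51990, 51992/59.5/OTSD0ZZ, OTSD4ZZ Laparoscopic urethral suspension, laproscopic sling procedure".
- **Outcome, Re-Operation:** "Laparoscopic Retropubic Urethropexy CPT 51990, 51992, 51999".

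The row for SUI with Mesh has a single entry: "Admin Codes CPT 57288".

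Section 4 describes non-mesh surgery as fascial slings (autologous or cadaveric), Burch colposuspension or bulking agents. Section 6 has a shorter list, autologous fascial sling or Burch. Neither names a laparoscopic sling. Section 5 admits "All women aged 18 or greater undergoing transvaginal surgery for stress urinary incontinence (index surgery) with or without mesh implantation". Section 8.1 has sites add "free text peri-operative documents for those patient cases that has mesh implantation for stress urinary incontinence" to the structured data.

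**The concern.** A code that denotes a sling but not its material is assigned outright to the non-mesh group. Sections 4 and 9.1 have the same outcomes evaluated in that group and shown beside the mesh group, and Section 3 says the FDA intends to use the results when judging level of risk. A synthetic sling filed as non-mesh would do two things. Its erosions and removals would count in the column meant to describe surgery without mesh. The woman would also be missing from the risk model of Section 3, aim 4, which is confined to patients receiving mesh. Separately, the same code is called a sling in two rows and a urethropexy in a third, so the programmer has no single definition to implement.

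**Working it through.** The plan states no figure on this point, so the check compares the code lists with the text and then gives a scale calculation.

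**1. Where the lists send 51992.**

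| List | CPT codes |
|---|---|
| Inclusion row | 57288, 51992 |
| SUI with Mesh | 57288 |
| SUI without Mesh | 51715, 51990, 51992, 51840, 51841, 51845, 57220 |

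51992 is on the non-mesh list and not on the mesh list, and no condition on material is attached. Under the Synopsis rule, every 51992 case is therefore non-mesh.

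**2. Whether the text supports that.** Under Section 4 a sling is non-mesh only if it is fascial. The 51992 entries give no material. The one sling code whose material the appendix describes, 57287, covers both fascial and synthetic slings. So there are two cases:

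- The 51992 sling is fascial: the code rule and Section 4 agree.
- The 51992 sling is synthetic: the code rule says non-mesh and Section 4 does not. Because Section 4 defines the mesh exposure as slings placed transvaginally, a synthetic sling placed laparoscopically may belong in neither group.

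**3. Whether a later step would correct it.**

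- *Operative-note extraction (Section 8.1)* is limited to mesh cases. A 51992 case has already been classed as non-mesh, so its note is not pulled.
- *Chart review (Section 6)* covers 50 to 100 cases per site, or 250 to 500 over five sites. It is a validation sample. It can reveal an error but does not reclassify the cohort, and nothing says that 51992 cases will be in it.
- *Device implantation data (Section 4)* are named as a source for finding sling patients, but no rule says they override the CPT row. Section 11 does not expect device-specific information to be available.

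**4. The urethropexy label.** In the Re-Operation row, 51992 counts as a re-operation under either name. The total is unchanged. Only a breakdown by type of repeat surgery would be affected.

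**5. Scale, for illustration only.** Let *f* be the share of the non-mesh group that consists of synthetic slings coded 51992. The protocol does not give *f*, so it is assumed here. Section 1.1 quotes 1.6% erosion requiring intervention (New York registry, SUI surgery) and 3.3% mesh removal at 9 years (UK cohort).

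Added erosions per 1,000 = 1,000 × *f* × 0.016
Added removals per 1,000 = 1,000 × *f* × 0.033

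| *f* | Erosions per 1,000 | Removals per 1,000 |
|---|---|---|
| 0 (all fascial) | 0 | 0 |
| 1% | 0.16 | 0.33 |
| 5% | 0.8 | 1.65 |
| 20% | 3.2 | 6.6 |
| 100% | 16 | 33 |

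The removal column probably overstates what would be seen, because with data from 2010 to 2019 only women operated on near the start could be followed for 9 years.

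**The case against.** The strongest reply is that none of this shows a single misfiled sling. A reader might infer that laparoscopic slings are synthetic and that their erosions will therefore be reported as harm of non-mesh surgery. The documents do not support that step: they state neither the material nor the number of 51992 cases, and the preliminary volume query covered 57288 only. If all are fascial, the non-mesh row is right. This objection stands, and it makes the point conditional.

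Other replies also stand in part:

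- A code can serve for both inclusion and non-mesh exposure without contradiction. The inclusion row separates SUI from prolapse, and the cohort takes surgery with or without mesh.
- It is tempting to say that Section 5 rules out 51992 because it is not transvaginal. The same argument would remove 51990 and the Burch-type codes 51840 and 51841, yet Section 4 names Burch as an intended comparator. The tension is between Section 5 and much of the comparator definition.
- One might infer that 51992 is the entire comparator, as the only code on both the inclusion and the non-mesh lists. Sections 4 and 6 show that this is not intended.
- Mesh-type events need not be close to zero in the non-mesh group even without this problem. The Mesh Erosion row also lists codes for infection, transfusion and urinary retention, and 57287 covers fascial slings.
- It would be wrong to say these cases are never checked, since chart review and device data exist.
- Sections 4 and 9.1 exclude a formal comparison of the groups, so no test result is at risk.

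None of these replies supplies a rule for setting mesh status when the code does not show the material.

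**Conclusion.** The point holds as a flaw in the exposure rule. As written, 51992 slings are classed as non-mesh irrespective of material, against Section 4's restriction to fascial slings, and the planned note extraction does not reach them. The consequence is confined to the descriptive side-by-side rates and to membership of the mesh-only risk model, and it arises only for 51992 slings that are synthetic.

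The size cannot be determined from the protocol. The calculation above rests on an assumed share and on rates from other populations. It shows scale only and does not estimate bias. The urethropexy label is a real inconsistency with no demonstrated effect on event totals. The point still merits correction before extraction, because it affects a key exposure and costs little to settle.

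**What to change.** 1. Remove 51992 from the automatic SUI without Mesh list.
2. Choose one of two treatments and state it. Either drop 51992 from the inclusion row as not transvaginal, or keep it and assign mesh or fascia from the operative note or device data. The second option requires extending the Section 8.1 note extraction to 51992 cases and stating which source prevails when they disagree.
3. Label 51992 as a sling in the Re-Operation row.
4. Separately, reconcile the transvaginal criterion in Section 5 with the other laparoscopic and abdominal comparator codes (51990, 51840, 51841).
5. Report the number of 51992 cases per site, so that the reader can see whether the issue matters.

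The cost is a few appendix edits with the matching change to the extraction code and, if the code is kept, note review for the 51992 cases.

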Outcome	Re-Operation	 CPT code based Reoperation for Mesh Revision/Removal sling revision/removal-CPT codes 57287, 10120 Removal of Autologous Tissue Substitute from Urethra, Open Approach (ICD 10 PCS 0TPD07Z). Removal of Synthetic Substitute from Urethra, Open Approach (ICD 10 PCS 0TPD0JZ). Removal of Nonautologous Tissue Substitute from Urethra, Open Approach (ICD 10 PCS 0TPD0JZ). Revision of Autologous Tissue Substitute in Urethra, Open Approach (ICD 10 PCS 0TWD07Z). Revision of Autologous Tissue Substitute in Urethra, Open Approach (ICD 10 PCS 0TWD07Z). Revision of Synthetic Substitute in Urethra, Open Approach (ICD 10 PCS 0TWD07Z). Revision of Nonautologous Tissue Substitute in Urethra, Open Approach (ICD 10 PCS 0TWD07Z). Revision of Nonautologous Tissue Substitute in Urethra, Open Approach (ICD 10 PCS 0TWD0Z). Revision of Nonautologous Tissue Substitute in Urethra, Open Approach (ICD 10 PCS 0TWD0KZ). Reoperation for Mesh Revision/Removal Subtypes: Hemorrhage/bleeding (ICD9/10 459.0, 998.11, 623.8 or 596.89/ R58, N99.820, N99.821) Nerve injury (ICD9/10 956.3, 956.5, 956.8, 956.9, 957.9/S30-S39, S84.10XA, S74.8X9A) Pain (ICD9/10 338,338.1,338.2, 338.21, 	Yes	revision, incision, excision, removal. Represented as a Date, allows time-to-event analysis. Some of the covariate & outcome variables pertaining to degree of recurrence (may not be ascertainable in structured data, will require text search), including urinary urgency as a symptom (depends on the pre-operative visit, under-documented in structured data)

Protocol 1		1		[15 July 2020]

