Outcome	Mesh Erosion	Admin Codes: ICD-9-CM codes for mesh erosion: 996.30, 996.39, 996.59, 996.60, 996.65, 996.69, 996.70, 996.76, 996.79, 939.0, 939.2, and 939.9 ICD 10 CM: T83.498A, T85.698A, T85.79XA, T83.598A, T85.79XA, T85.9XXA, T83.89XA, T85.898A, T19.0XXA, T19.2XXA, T19.9XXA Surgical Complications: ICD 9/10 629.31/T83.711 Erosion of implanted vaginal mesh ICD 9/10 629.32/T83.721S Exposure of implanted vaginal mesh ICD 9/10 996.76/T83.9 Complication of genitourinary device, implant or graft ICD9/10-PCS V58.2/30233N1, 30233P1, 30233H1 Blood transfusion ICD9/10 998.5/ T81.49XA, T81.40XS, T81.41, T81.43, T83.5, T83.6 Postoperative infection ICD 9/10 778.2/R33.9 Urinary retention		Capture as date/time Exclude 629.3- complication of implanted vaginal mesh and other prosthetic materials, 629.31- erosion of implanted vaginal mesh, or 629.32-exposure of implanted vaginal mesh because these ICD-9 were not released until 2011? ²⁸ SME determined that topical estrogen could be prescribed for other reasons
Outcome	Urethral fistula	Admin Codes ICD 9- 599.1 ICD 10-N36.0	Yes	Capture as date/time
Covariate	Prior Abdominal Surgery Or Pelvic Radiation	Admin Codes: Personal history of irradiation-V15.3/Z92.3, Irradiation cystitis- N30.4	Yes	Yes/No
	Therapy	CPT/ICD 9/ICD 10 for prior abdominal surgery:		

Protocol 1		[15 July 2020]
	Hysterectomy: 00846, 00855, 00944, 01962,	
	01963, 01969,45126, 51597, 51925, 56308,	
	58150, 58152, 58180, 58200, 58205, 58210,	
	58240, 58260, 58262, 58263, 58265, 58267,	
	58270, 58275, 58280,	
	58285, 58290, 58291, 58292, 58293,	
	58294, 58541, 58542, 58543, 58544,	
	58548, 58550, 58552, 58553, 58554,	
	58570, 58571, 58572, 58573, 58575,	
	58951, 58953, 58954, 59135,	
	59525, 59560, 59561, 59580, 59581	
	/68.9/290.711	
	Cesarean section: 00850, 59500, 59501,	
	59520, 59521, 59540, 59541/649.81/075.82	
	Appendectomy: 44950, 44955, 44960,	
	44970, 49315, 56315/V45.79/Z90.89	
	Hernia repair: 49505, 49507, 49520,	
	49521, 49525, 49550, 49553, 49555,	
	49557, 49560, 49561, 49565, 49566,	
	49570, 49572, 49585, 49587, 49590,	
	49650, 49651, 49652, 49653, 49654,	
	49655, 49656, 49657, 49659/53.5/0WQF0ZZ,	
	0WQF3ZZ, 0WQF4ZZ	
	Cholecystectomy: 47562, 47563, 47564, 47600,	
	47605, 47610, 47612, 47620/51.0-	
	51.04/0FT40ZZ	
	51.04/01 14022	
	Colectomy: 44139, 44140, 44204, 44205, 44206,	
	44141, 44143, 44144, 44145, 44146, 44147,	
	44150, 44151, 44157, 44158, 44160,44320,	
	44322, 44799, 45110, 45111, 45112, 45113,	

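### In ICD-10 data the nerve-injury subtype of re-operation takes in the list's own bowel and bladder/urethral injury codes, and the infection and ICD-10-PCS entries beside it need reconciling

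*Protocol*

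**What the plan says.** The Data Collection table in Section 13 (Appendices) defines the Re-Operation outcome by procedure codes. It then lists diagnosis subtypes for re-operations that revise or remove mesh. Three of these are:

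- "Nerve injury (ICD9/10 956.3, 956.5, 956.8, 956.9, 957.9/S30-S39, S84.10XA, S74.8X9A"
- "Bowel injury (ICD9/10 569.83/S36"
- "Bladder/urethral injury (ICD9/10 596.6,867.0/S37"

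A fourth is "Infection (ICD9/10 686.9,998.5,999.3,998.51,998.59/T81". The Mesh Erosion row of the same table has its own postoperative infection entry, which pairs ICD-9 998.5 with "T81.49XA, T81.40XS, T81.41, T81.43, T83.5, T83.6 Postoperative infection".

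The procedure part of the Re-Operation row opens with CPT 57287 and 10120 and goes on to ICD-10-PCS codes by graft material. Among them are "Removal of Autologous Tissue Substitute from Urethra, Open Approach (ICD 10 PCS 0TPD07Z", "Revision of Autologous Tissue Substitute in Urethra, Open Approach (ICD 10 PCS 0TWD07Z" and "Revision of Synthetic Substitute in Urethra, Open Approach (ICD 10 PCS 0TWD07Z".

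Section 7 defines the primary outcome as re-operation or mesh removal, pooled over causes. Section 4 notes that the data cover both the ICD-9 and the ICD-10 periods.

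**The concern.** A subtype should mean the same thing whichever coding system was in use when the patient was re-operated. On the ICD-9 side, nerve injury is five specific codes. On the ICD-10 side it is a ten-category block that includes injuries the list itself classes as something else. A programmer following the table would mark a bladder perforation coded S37 as a nerve injury, and would not do so for the same event coded 867.0. A site-level count of nerve-injury re-operations could then move with the coding system alone.

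Section 9.1 promises counts of each outcome at each site. Section 11 says that definitions and transformation code will be shared. An error in the table would therefore reach the reports and could be reused by others. The infection and PCS entries raise the same question: can the table be programmed as printed without giving inconsistent results?

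**Working it through.** No figure in the plan has to be reproduced. The check is a comparison of the code lists in Section 13.

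**1. Nerve, bowel and bladder/urethral injury**

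| Subtype | ICD-9 | ICD-10 |
|---|---|---|
| Nerve | 956.3, 956.5, 956.8, 956.9, 957.9 | S30-S39, S84.10XA, S74.8X9A |
| Bowel | 569.83 | S36 |
| Bladder/urethral | 596.6, 867.0 | S37 |

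- ICD-9: nerve and bowel have no code in common, and nerve and bladder/urethral have none.
- ICD-10: S30-S39 is S30, S31, …, S39. It contains both S36 and S37.
- Result: in ICD-10 data, all re-operations flagged as bowel or bladder/urethral injury are also flagged as nerve injury. In ICD-9 data these lists produce no such overlap.

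**2. Infection**

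| Row | ICD-9 | ICD-10 |
|---|---|---|
| Re-Operation subtype | 686.9, 998.5, 999.3, 998.51, 998.59 | T81 |
| Mesh Erosion, postoperative infection | 998.5 | T81.49XA, T81.40XS, T81.41, T81.43, T83.5, T83.6 |

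Neither ICD-10 list contains the other. Bare T81 takes in the whole category, of which the second list uses only T81.4x codes. T83.5 and T83.6 lie outside T81.

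**3. ICD-10-PCS material codes, as printed**

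| Code | Printed for |
|---|---|
| 0TPD07Z | removal, autologous |
| 0TPD0JZ | removal, synthetic; removal, nonautologous |
| 0TWD07Z | revision, autologous (twice); revision, synthetic; revision, nonautologous |
| 0TWD0Z | revision, nonautologous |
| 0TWD0KZ | revision, nonautologous |

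The sixth character appears to denote the material: 7 autologous and J synthetic among the removal codes, K on one nonautologous revision line. On that pattern one would look for 0TWD0JZ (synthetic revision) and 0TPD0KZ (nonautologous removal). Neither is printed. 0TWD0Z has six characters where the others have seven, so a character has been lost somewhere.

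**The case against.** The strongest reply is that little rests on these subtypes. Section 7 pools re-operation over causes. The aims in Section 3 link re-operation to pain and to voiding symptoms, and do not name nerve, bowel or bladder injury. The subtypes are nowhere said to be mutually exclusive. Most of this stands and limits the consequence. It does not rescue the nerve-injury entry: even with overlapping flags allowed, the list's own ICD-9 side does not treat a bowel or bladder injury as a nerve injury.

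Several stronger readings are tempting, and the documents do not support them.

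- **That cause-specific re-operation rates are wrong in general.** The overlap enlarges only the nerve-injury subtype, and only in ICD-10 data. The bowel and bladder/urethral definitions are unchanged. The PCS codes identify a procedure, not its cause, so an error there could lower capture but could not misassign cause.
- **That synthetic-sling revisions are not captured.** The Mesh Removal row describes CPT 57287 as covering both fascial and synthetic slings, so a revision with that code is counted whatever the PCS line says. The PCS revision lines also repeat themselves and include the six-character code, and the retropubic hematoma line nearby is printed three times. Damage in text extraction is a real possibility, and the missing character could be the J. The three removal lines each appear once, so extraction is a less likely explanation for the duplicate 0TPD0JZ. CPT 57287 is not complete either: the same row warns that some surgically managed erosions may carry another CPT.
- **That the share of follow-up under ICD-10 measures the error.** Assume uniform surgery dates over 2010-2019, no censoring and a switch on 1 October 2015 (not in the protocol). The share is then 1 − (5.75²/2)/(10²/2) = 1 − 16.5/50 = 67%. Beyond two years it is 1 − (3.75²/2)/(8²/2) = 1 − 7.03/32 = 78%. These are shares of person-time. They are not shares of re-operations misflagged, and Section 9.1 does plan censoring.
- **That ICD-9 459.0 under both hemorrhage and retropubic hematoma is a mistake.** With flags that need not exclude each other, a hematoma may also count as bleeding. No error is shown.

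**Conclusion.** The point holds for the nerve-injury subtype. As written, every ICD-10 re-operation with a listed bowel or bladder/urethral injury code is also a nerve-injury re-operation, and the subtype means different things in the two coding eras. This assumes that a category or block in the table stands for all codes beneath it, which is the ordinary reading. The number of re-operations affected cannot be computed, because the documents give no counts by diagnosis.

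The two infection definitions are a plain inconsistency within the appendix. The documents do not show how far their counts would differ.

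The PCS entries are inconsistent as printed and may lower capture of re-operations that carry no CPT 57287. Whether the fault lies in the protocol or in the extracted text has to be settled from the PDF.

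The correction is worth making before the extraction code is written or reused. It does not call the primary outcome into question.

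**What to change.** - **Nerve injury:** replace S30-S39 with nerve-specific ICD-10 codes that match the ICD-9 956.x and 957.9 list. Keep S36 only under bowel injury and S37 only under bladder/urethral injury.
- **Infection:** use one ICD-10 definition in the Re-Operation and Mesh Erosion rows. Narrowing T81 to T81.4x alone would drop T83.5 and T83.6, so decide on those two explicitly.
- **ICD-10-PCS:** check the material characters on the removal and revision lines against the source PDF and the code book, and correct them where they are wrong.
- **Both groups:** apply the same outcome codes to mesh and non-mesh patients. Restricting the autologous codes to the non-mesh group would make the outcome depend on exposure, whereas Section 4 plans to evaluate the same outcomes in both.

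The cost is a few entries in the appendix table and the matching lines of the extraction code. No new data are needed.
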